9.3.3 ANALYSIS OF THE SECONDARY ENDPOINT(S)

Analysis of secondary endpoints are not dependent on findings of primary endpoint.

-% weight loss: at month 6

-Physical activity: ≥10% increase in total minutes/week of physical activity based on IPAQ at month 6

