3 OBJECTIVES AND ENDPOINTS

OBJECTIVES	ENDPOINTS	JUSTIFICATION FOR ENDPOINTS
Primary		
Compare the effectiveness of usual care to a mobile technology based lifestyle intervention on change in liver and metabolic related parameters.	Reduction in amount of hepatic steatosis (≥5% overall reduction in CAP score) at 6 months.	Hepatic steatosis is a liver specific outcome that has been shown to improve with diet and exercise and is associated with risk of downstream clinical outcome such as development of NASH and cirrhosis.
Secondary		

OBJECTIVES	ENDPOINTS	JUSTIFICATION FOR ENDPOINTS
Improvements in other liver-specific and metabolic outcomes	weight loss, increase in total physical activity (based on step counts)	Weight loss has been associated with histologic improvements in NAFLD and NASH. Physical activity has been shown to improve fibrosis, liver enzymes, metabolic parameters and HRQOL.

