4 STUDY DESIGN

4.1 OVERALL DESIGN

This randomized clinical pilot trial will compare a mobile technology-based lifestyle intervention to a waitlist control group receiving usual care for adult patients with NAFLD. The intervention will use FitBit to track and promote physical activity through tailored longitudinal feedback. Patient will also receive nutritional counseling with serial nutritional assessments. The primary endpoint will be change in amount of hepatic steatosis. Secondary outcomes include changes in weight and physical activity (assessed by trend in step counts). A wait-list control design will be applied. 60 Patients will be randomized to the intervention arm for 6 months and 60 to usual care (the wait-list control). Those initially randomized to the intervention arm will then transition to a 6-month post intervention monitoring period to assess maintenance of behavior change and sustainability of impact on outcomes of interest. Individuals initially randomized to usual care, will transition to the intervention at month 6 for a total of 6 months.

The intervention arm will receive tailored physical activity and nutritional counseling, and the waitlist control arm which will follow usual and customary care for NAFLD patients attending our Heptology clinic for 6 months and then receive the 6-month intervention.

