4.3 JUSTIFICATION FOR INTERVENTION

Multiple studies in general obesity research and specifically among patients with NAFLD have shown that patients should aim to achieve ≥150 min/week of moderate intensity physical activity. For diet, the majority of studies have recommended a total caloric reduction of 30% in obese and overweight patients in order to achieve weight loss. We will track total amount of physical activity time and change in nutritional content as part of this intervention.

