5 STUDY POPULATION

5.1 INCLUSION CRITERIA

In order to be eligible to participate in this study, an individual must meet all of the following criteria:

- 1. Provision of signed and dated informed consent form
- 2. Stated willingness to comply with all study procedures and availability for the duration of the study
- 3. Age 18 or older
- 4. Diagnosis of NAFLD or NASH based on: liver biopsy (within past 24 months) or imaging [ultrasound (US), vibration controlled transient elastography (VCTE), cat scan (CT), or magnetic resonance imaging (MRI)] within past 24 months
- 5. Ability to communicate in English as their primary language.
- 6. Access to mobile phone/tablet/ or computer compatible with FitBit application and ability to use said device and application.
- 7. Ability to participate in physical activity (reports ability to walk at least several blocks unassisted).

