6 STUDY INTERVENTION(S) OR EXPERIMENTAL MANIPULATION(S)

6.1 STUDY INTERVENTION(S)

6.1.1 STUDY INTERVENTION OR EXPERIMENTAL MANIPULATION DESCRIPTION

This is a randomized trial comparing a structured mobile technology-based lifestyle intervention compared to usual care.

Intervention

-Education: Patients in the intervention arm will receive our NAFLD educational folder with an overview of contents by study staff. The folder includes: 1) NAFLD disease information including diagnosis, clinical manifestations, natural history and treatments; 2) NAFLD nutritional recommendations including sample menus; 3) NAFLD physical activity recommendations including walking programs and physical activity logs; 4) weight tracking logs; and 5) resources for diet and exercise programs.

-**Physical Activity**: All participants in the intervention arm (N=60) will receive a FitBit Zip for monitoring of step counts. The Fitbit wirelessly syncs data from the tracker to the Fitbit software or app. Study staff will assist with downloading the software and will instruct participants to wear their FitBit during waking hours every day. At any time if the participant has questions or problems regarding the use of the FitBit, a study staff member can be contacted. Study staff will retrieve users' step count data for analysis weekly and will provide subject with personalized feedback on physical activity with tailored step count goals (10% increase per week with max increase 800 steps per week to a maximum of 10,000 steps/week) and motivational messaging via e-mail. Patients with consecutive days without data recorded or with other signs of low FitBit usage (days with minimal step counts) will be contacted by study staff via e-mail or phone if necessary to encourage use. Feedback will occur weekly for the first 3 months of the intervention and then transition to biweekly for the last 3 months. Participants will also complete the short-version IPAQ for physical activity at enrollment, 6 month and 12 month follow-up visits.

-Nutrition: Patients in the intervention arm will have a nutritional assessment by a GI nutritionist specializing in NAFLD either at the enrollment visit if time allows, or in a separate in person or phone assessment within the first 2 weeks of enrollment. All patients will also complete the "Starting the Conversation" nutritional questionnaire for patients with metabolic disease at enrollment, 6 month and 12 month follow-up visits.(15)

Usual Care

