6.3 MEASURES TO MINIMIZE BIAS: RANDOMIZATION AND BLINDING

Participants in this trial will be randomized to either the intervention arm (tailored physical activity and nutritional counseling) or a wait-list control arm that receives usual care for 6 months, after which they will receive the intervention (for 6 months). Neither participants nor interventionists are blinded to study arm.

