9.2 SAMPLE SIZE DETERMINATION

Sample size calculations will be made based on the total N for the cohort. Enrollment of 120 patients in the intervention should provide adequate power to assess for parameters associated with \geq 5% reduction in steatosis and weight loss using 80% power, alpha 0.05. We anticipate a dropout rate of up to 20%.

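### The physical-activity endpoint, a ≥10% rise over the patient's own IPAQ minutes, is undefined at a zero baseline, sets an uneven bar elsewhere and loses power

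*Combined protocol and SAP*

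**What the plan says.** Section 9.3.3 gives the physical-activity criterion as "≥10% increase in total minutes/week of physical activity based on IPAQ at month 6". It names no test, gives no reason for the 10% cut and sets no minimum absolute change. It does not say what happens when baseline minutes are zero.

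The instrument is a self-completed questionnaire. Section 6.1.1 states: "Participants will also complete the short-version IPAQ for physical activity at enrollment, 6 month and 12 month follow-up visits". The schedule tables in Section 1.3 place the IPAQ at Visits 1 and 2 in both arms. On blinding, Section 6.3 says: "Neither participants nor interventionists are blinded to study arm".

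The only activity-related entry criterion, in Section 5.1, is "Ability to participate in physical activity (reports ability to walk at least several blocks unassisted". It sets neither a minimum nor a maximum for baseline activity. Section 4.3 justifies the intervention by saying "patients should aim to achieve ≥150 min/week of moderate intensity physical activity".

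Two other sections define the outcome differently. Section 3 lists "weight loss, increase in total physical activity (based on step counts", and Section 4.1 says "Secondary outcomes include changes in weight and physical activity (assessed by trend in step counts". Section 9.1 hypothesises more activity at 6 months than under usual care but names no instrument.

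**The concern.** The criterion is a ratio to the patient's own baseline, which creates three separate difficulties.

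- At zero minutes there is no ratio. Someone must decide whether these patients are dropped, counted as failures, or counted as responders. With no written rule, that choice would be made with the data in hand, in an unblinded trial with a self-reported measure.
- At low non-zero baselines a few reported minutes make a responder, while at high baselines a gain of half an hour may not. Going from 20 to 22 passes; going from 400 to 430 fails.
- Splitting a continuous quantity at a cut close to no change discards information.

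At stake is the activity part of the secondary hypothesis in Section 9.1. The result could depend on an unwritten scoring choice, and a real difference would be harder to detect than the collected data allow.

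**Working it through.** **What can be reproduced.** The plan gives no design figure for physical activity. The statement in Section 9.2, "using 80% power, alpha 0.05", refers to factors associated with steatosis reduction and weight loss. It gives no effect size, SD or event rate, so 120 cannot be re-derived. What follows uses 60 per arm (Section 4.1), dropout up to 20% (Section 9.2) and a two-sided 0.05 test (Section 9.3.1). Evaluable patients: 60 × (1 − 0.20) = 48 per arm, 96 in total.

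**1. The bar by baseline.** Gain needed = 0.10 × baseline minutes/week.

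| Baseline | Gain needed | Gain as share of 150 |
|---|---|---|
| 0 | undefined | – |
| 10 | 1 | 0.7% |
| 20 | 2 | 1.3% |
| 60 | 6 | 4% |
| 150 | 15 | 10% |
| 400 | 40 | 27% |
| 600 | 60 | 40% |

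If the rule is programmed as follow-up ≥ 1.1 × baseline, the threshold at zero is zero, so a patient who stays at 0 counts as a responder.

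**2. How many have a zero baseline.** The documents do not say. An assumed 5% to 30% gives 6 to 36 of 120 enrolled, or about 5 to 29 of 96 evaluable. A share near zero would make this part negligible.

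**3. Effect of the unwritten rule.** Assumed: 20% at zero in each arm; responders among the rest 40% (control) and 65% (intervention); zero-baseline patients who become active 25% and 60%.

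Power = Φ{[Δ − 1.96 √(2p̄(1−p̄)/n)] / √([pc(1−pc) + pt(1−pt)]/n)}, where pc and pt are the control and intervention rates, Δ = pt − pc, p̄ is their mean and n is the number per arm.

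| Rule for zero baselines | n per arm | Rates | Power |
|---|---|---|---|
| Excluded | 48 × 0.8 = 38.4 | 40% vs 65% | 60% |
| All non-responders | 48 | 0.8 × 40 = 32% vs 0.8 × 65 = 52% | 51% |
| 1.1 × baseline taken literally | 48 | 32 + 20 = 52% vs 52 + 20 = 72% | 52% |
| Any minutes above zero | 48 | 32 + 5 = 37% vs 52 + 12 = 64% | 76% |

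With no zero-baseline patients it would be 69.5%.

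**4. Response with no true change (non-zero baselines).** Let s be the SD of the within-patient change in log minutes. Then P(≥10% rise) = 1 − Φ(ln 1.1 / s). For assumed s from 0.2 to 1.0 this runs from 32% to 46%. At s = 0.5: 1 − Φ(0.0953/0.5) = 42%.

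**5. Cost of the cut (non-zero baselines, 48 per arm, true increase 30% in the intervention arm only).** At s = 0.5:

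- Responder cut: intervention rate 1 − Φ((ln 1.1 − ln 1.3)/0.5) = 63% against 42%. The formula in step 3 gives 53%.
- Mean log change: Φ(ln 1.3 / (0.5 √(2/48)) − 1.96) = Φ(0.2624/0.1021 − 1.96) = Φ(0.61) = 73%.

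Other assumed values of s:

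| s | Responder cut | Mean log change |
|---|---|---|
| 0.3 | 92% | 99% |
| 0.5 | 53% | 73% |
| 0.7 | 31% | 45% |
| 1.0 | 17% | 25% |

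The continuous analysis here is a comparison of mean log change. It stands in for the baseline-adjusted rank-based or robust analysis recommended below, whose power was not calculated.

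**The case against.** The strongest reply is that only a scoring rule is missing, for one of two secondary endpoints in a pilot, and one added sentence would supply it. Section 9.1 speaks of patients being more likely to increase activity, which suits a proportion. Section 9.3.1 already allows nonparametric tests. The zero share and the noise level are assumptions.

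Much of this stands. The number of patients affected is unknown, and the primary endpoint and sample size do not depend on this measure. But the nonparametric sentence does not help: responder status must exist before it can be tested, and 9.3.3 does not commit to analysing the minutes themselves. A one-line rule would also leave the uneven bar and the loss of power, which the same questionnaire data could avoid.

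Four stronger readings may tempt a reader, and the documents do not support them.

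- *The programme is aimed at inactive patients, so the rule fails its target group.* Section 5.1 sets no ceiling on activity and no section describes an inactive target group. Zero-minute reporters can enrol; nothing more can be said.
- *The threshold is trivial.* That holds only at low baselines; at 150 it is 15 minutes/week and at 600 it is 60.
- *Recall noise biases the comparison.* In the model above, noise raises the responder rate equally in both arms. It costs power but favours neither arm. Unblinded self-report could favour one, but that is a different matter, and changing the analysis would not cure it.
- *Reaching 150 minutes/week is the obvious replacement.* Section 4.3 refers to moderate-intensity activity, whereas 9.3.3 counts all minutes. Attainment also credits patients already above 150 who did not change, while 9.1 hypothesises an increase.

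**Conclusion.** The concern holds within limits. From the documents alone, the ≥10% criterion is undefined at zero minutes, such patients are eligible, no scoring rule exists, and the required gain runs from 2 minutes/week at a baseline of 20 to 40 at 400. Zero-baseline patients are unclassified rather than misclassified; low non-zero patients are classified, but too easily as responders.

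The loss of power is certain in direction for a shift of the kind modelled, but its size is only illustrative: about 53% against 73% at an assumed log-change SD of 0.5 and a true increase of 30%. With an assumed 20% at zero, the choice of scoring rule alone moves power between 51% and 76%. No figure in the documents fixes these inputs.

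The change is worth making before analysis. The documented conflict between IPAQ minutes in 9.3.3 and step counts in Sections 3 and 4.1 must be resolved with it; otherwise the work may refine a measure that is not the endpoint.

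**What to change.** In Section 9.3.3:

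1. Make the comparison between arms month-6 IPAQ minutes/week adjusted for baseline minutes, in a named rank-based or robust model. Zero is then an ordinary value and zero-baseline patients stay in.
2. Keep the ≥10% responder rate as supportive only, and write the zero-baseline rule before the data are analysed.
3. If the proportion reaching 150 minutes/week is reported, count moderate-intensity minutes only, as in Section 4.3, adjust for baseline status and label it descriptive.
4. Reconcile 9.3.3 with Sections 3 and 4.1, stating whether IPAQ minutes or step counts is the secondary endpoint. The IPAQ is scheduled in both arms at Visits 1 and 2, so the comparison in item 1 needs no new data.

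The cost is wording: same questionnaire, same visits, no extra patients. The downside is a result less simple to state than a responder percentage, which the supportive rate partly offsets.

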4.2 SCIENTIFIC RATIONALE FOR STUDY DESIGN

This trial will incorporate a wait-list control that will allow us to maximize our ability to assess the primary outcome (by using a pre-post intervention analysis). The 6-month post-intervention follow-up among those initially randomized to the intervention will allow us to assess maintenance of behavior change.

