9 STATISTICAL CONSIDERATIONS

9.1 STATISTICAL HYPOTHESES

Primary Efficacy Endpoint:

We hypothesize that participants who complete the lifestyle intervention (as defined by completing the 6 month return visit and data collection) will achieve reduction in amount of hepatic steatosis (\geq 5% reduction in CAP), with those achieving higher percentage weight loss having larger reductions in amount of steatosis.

Secondary Efficacy Endpoints:

We hypothesize that subjects in the intervention arm will be more likely to achieve weight loss and increase their level of physical activity at 6-month compared to usual care.

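### The physical-activity secondary endpoint is step counts in Sections 3 and 4.1 but IPAQ minutes in Section 9.3.3. No section says which governs, and IPAQ is the better-supported basis for the month-6 comparison with usual care.

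*Combined protocol and SAP*

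**What the plan says.** Section 1.1 lists change in physical activity as a secondary endpoint and names no instrument. The endpoint table in Section 3 gives "increase in total physical activity (based on step counts". Section 4.1 agrees: "Secondary outcomes include changes in weight and physical activity (assessed by trend in step counts". Section 9.3.3 instead analyses a 10% or greater "increase in total minutes/week of physical activity based on IPAQ at month 6".

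The hypothesis in Section 9.1 is comparative. The intervention arm is expected to be more likely to "increase their level of physical activity at 6-month compared to usual care".

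On data collection, Section 6.1.1 says "All participants in the intervention arm (N=60) will receive a FitBit Zip for monitoring of step counts". The usual-care description in the same section mentions no tracker. Section 4.1 adds "Individuals initially randomized to usual care, will transition to the intervention at month 6 for a total of 6 months", and Section 6.3 and the Table 2 caption give the same order. Section 6.1.1 also says "Participants will also complete the short-version IPAQ for physical activity at enrollment, 6 month and 12 month follow-up visits". The IPAQ row is marked at Visits 1, 2 and 3 in both Table 1 and Table 2.

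**The concern.** The two definitions answer different questions. IPAQ at month 6 can be compared between randomised arms while the wait-list arm is still on usual care, which is what Section 9.1 asks for. Step counts, provided as Section 6.1.1 describes, show change while on the intervention, with no concurrent control.

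With both in current text and neither ranked, either could be reported as the prespecified endpoint, and the choice could be made once results are known. If Sections 3 and 4.1 were followed as written, the physical-activity hypothesis in Section 9.1 could be left without a control group.

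**Working it through.** The plan gives no figure to reproduce. The sample-size statement in Section 9.2 has no effect size, standard deviation or response rate, and is not tied to physical activity. The check is therefore a comparison of texts.

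Step 1: compare the definitions.

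| Feature | Sections 3 and 4.1 | Section 9.3.3 |
|---|---|---|
| Instrument | Tracker | Self-reported questionnaire (IPAQ) |
| Unit | Steps | Minutes per week |
| Form | Increase, or trend | Responder at 10% or more |
| Time point | None given for physical activity | Month 6 |

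They differ in instrument, unit and form, and only Section 9.3.3 gives instrument, unit, threshold and time point together. Section 4.3 also says that time spent in physical activity will be tracked, which fits a minutes-based measure. No section calls one definition primary and the other supportive.

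Step 2: ask which measure exists in both arms in months 0-6, as Section 9.1 requires.

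- IPAQ: marked at Visit 1 and Visit 2 in both tables, so 60 + 60 = 120 participants as planned.
- Step counts, intervention arm: 60 as planned (Section 6.1.1).
- Step counts, wait-list arm: 0 planned under Sections 6.1.1 and 6.3 and the Table 2 caption, because the tracker comes with an intervention that starts after Visit 2. If the Visit 1 mark in the FitBit row of Table 2 is taken literally, up to 60.

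Step 3: weigh the Table 2 mark. It conflicts with Section 6.1.1, with the caption, and with a row label that confines provision to the intervention arm. Table 1 carries the same Visit 1 and Visit 2 marks, although Visit 2 is when that arm moves from intervention to follow-up. A row copied between tables is plausible but not proven.

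Step 4: look for text that settles it. Section 6.4 has step data assessed weekly for every participant, but under an adherence heading and without naming an arm. Section 9.3.2 drops randomised participants who supply no FitBit data, again without naming an arm. Wait-list participants could supply such data in months 6-12, so neither statement shows that they hold trackers earlier.

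**The case against.** The best defence is that Section 9.3.3 is the analysis section and the only complete definition, so a reader would follow it, and that this is a secondary endpoint of a pilot. The first part is why IPAQ is the better choice, but no text gives Section 9.3.3 precedence over the endpoint table in Section 3. The second part limits severity only: Section 9.1 states a between-arm hypothesis, and Section 9.3.1 sets two-tailed tests at 0.05.

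It can also be said that Table 2 is trusted for IPAQ and doubted for the FitBit. This stands in part. Control-arm IPAQ before month 6 rests mainly on Table 2: the IPAQ sentence in Section 6.1.1 sits under the intervention, and the list in Section 8.1 omits IPAQ. The difference is that no text contradicts the IPAQ row, whereas several passages contradict the FitBit mark.

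A third defence is that the design intends a pre-post analysis, which step counts could serve. Section 4.2 does say "by using a pre-post intervention analysis", but about the primary outcome, and Section 9.1 compares physical activity with usual care.

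Three stronger readings are tempting and not supported:

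- A reader might infer that step counts cannot supply the month-6 comparison. The Table 2 Visit 1 mark is also current text, so the most that can be said is that no control step counts are planned under the other passages.
- A reader might infer that the lack of a step baseline before randomisation rules out a step comparison. By itself it does not, since randomised arms can be compared at month 6 without one.
- A reader might infer that the Section 9.3.2 exclusion would remove every control from the IPAQ analysis. That requires carrying a rule from the primary-endpoint section to this endpoint and counting FitBit data only up to month 6. The plan states neither.

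**Conclusion.** The point holds as an unreconciled conflict between two definitions of one secondary endpoint. Confidence in that conflict is high, since all the texts are current. Confidence that controls have no step counts in months 0-6 is moderate, because Table 2 disagrees with the text. The size is structural: 60 v 60 planned for IPAQ at month 6, against 60 intervention participants and either 0 or up to 60 controls for step counts. If trackers do go to controls at Visit 1, the conflict between definitions remains. The conclusion that IPAQ is the better basis assumes that the Table 2 IPAQ row means what it shows. The sponsor should correct this, though as a secondary endpoint it does not threaten the trial's main result.

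**What to change.** 1. In Sections 1.1, 3, 4.1 and 9.3.3, name the 9.3.3 IPAQ endpoint at month 6, compared between arms, as the single governing physical-activity secondary endpoint. Report step counts as a supportive measure during intervention periods.
2. Reconcile the Visit 1 FitBit mark in Table 2 with Section 6.1.1 and the Table 2 caption. If the sponsor confirms that controls hold trackers from Day 1, a between-arm step comparison may be added as supportive.
3. State that the Section 9.3.2 exclusion of participants without FitBit data does not apply to this comparison. That rule is worded for the final analysis generally, and membership of a between-arm analysis should not depend on a device that controls may not hold before month 6.

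The cost is wording in Sections 1.1, 3, 4.1, 9.3.2 and 9.3.3 and one table entry, with no new assessments. The downside is that IPAQ is self-reported and Section 6.3 leaves participants unblinded, so reporting bias could favour the intervention. Supportive step counts only partly offset this if controls have none before month 6.
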